9.4.2 Days 16–21

- Administer study drug:
 - IV infusion of study drug over 60 (± 10) minutes (refer to [Section 8.0](#) and the Study Pharmacy Manual for additional infusion rate guidance); administration should occur 24 (± 2) hours after study drug was administered on the previous day.

OR

- Oral step-down therapy.
- Clinical Assessments:
 - A focused physical exam (including a neurological exam) should be performed as clinically indicated by AE screening and course of the underlying disease.
 - Measure vital signs (temperature and the method used [oral, rectal, temporal, tympanic, or core], heart rate, blood pressure, and respiratory rate). Axillary temperatures are allowed, but not preferred.

- The retinal examination should be repeated in subjects who were negative at baseline if the subject develops visual signs or symptoms of a *Candida* eye infection during the study. Additionally, any neutropenic subjects who recover their neutrophil counts during the study should have an additional retinal examination. Subjects who were negative at baseline and are diagnosed with a *Candida* eye infection after initiating study drug must discontinue study drug (see [Section 7.4.2](#)) but may continue in the study at the Investigator's discretion; all subsequent antifungal drugs, interventions, and outcomes for endophthalmitis or chorioretinitis will be recorded.
- Laboratory Assessments:
 - Draw blood or normally sterile tissue/fluid (if possible) for culture if demonstrating mycological eradication (if not already done) or if clinically indicated.
 - Perform identification and susceptibility testing for *Candida* for any positive culture requiring a change of antifungal therapy (i.e., identification and susceptibility testing not required for *Candida* isolates cultured from specimens obtained without a required change in antifungal therapy).
 - All fungal isolates cultured from blood and normally sterile tissue/fluid must be sent to the Central Laboratory.
 - Record the spp. for any new bacteria isolated from blood and the spp. and susceptibilities for any new bacteria isolated from any other normally sterile site.
- Record all concomitant medications.
- Record AEs.
- Presence of central line during Screening or placed during the study should be documented with dates and times of insertion and removal.
- Short-term central venous catheters (e.g., peripherally-inserted central catheters, internal jugular, or subclavian central venous catheters) and long-term central venous catheters (e.g., tunneled catheters) are recommended to be removed within 48 hours after diagnosis with candidemia, consistent with IDSA ([Pappas 2016](#)) and ESCMID ([Cornely 2012](#); [Ullmann 2012](#)) guidelines.
- If radiologic test is performed, record radiologic test type with Findings and Interpretation only if radiologic test provides evidence of invasive candidiasis or evidence of progression, stabilization, improvement, or resolution of invasive candidiasis from previous radiographs. Criteria for cure, indeterminate, and failure responses are found in [Table 10](#).

9.4.3 Day 22 (± 1 day)

- One blood sample for PK will be collected pre-dose (≤ 30 minutes prior to the start of the infusion). Draw blood for PK analysis from the OPPOSITE arm or through an arterial line during the infusion; after the infusion is complete opposite arm or arterial line draws are preferred. For subjects receiving hemodialysis, an attempt should be made to obtain PK samples directly following hemodialysis if still within the required time window.
- Administer study drug:
 - IV infusion of study drug over 60 (± 10) minutes (refer to [Section 8.0](#) and the Study Pharmacy Manual for additional infusion rate guidance). Administration should occur 24 (± 2) hours after study drug was administered on the previous day.

OR

- IV infusion of study drug over 60 (± 10) minutes (refer to [Section 8.0](#) and the Study Pharmacy Manual for additional infusion rate guidance). Administration should occur 24 (± 2) hours after study drug was administered on the previous day PLUS oral step-down therapy.
- Clinical Assessments:
 - Conduct complete physical examination.
 - Conduct neurological examination as part of the physical examination, as clinically indicated.
 - Measure vital signs (temperature and the method used [oral, rectal, temporal, tympanic, or core], heart rate, blood pressure, and respiratory rate). Axillary temperatures are allowed, but not preferred.
 - The retinal examination should be repeated in subjects who were negative at baseline if the subject develops visual signs or symptoms of a *Candida* eye infection during the study. Additionally, any neutropenic subjects who recover their neutrophil counts during the study should have an additional retinal examination. Subjects who were negative at baseline and are diagnosed with a *Candida* eye infection after initiating study drug must discontinue study drug (see [Section 7.4.2](#)) but may continue in the study at the Investigator's discretion; all subsequent antifungal drugs, interventions, and outcomes for endophthalmitis or chorioretinitis will be recorded.
- Laboratory Assessments:
 - Draw blood or normally sterile tissue/fluid (if possible) for culture if demonstrating mycological eradication (if not already done) or if clinically indicated.
 - Perform identification and susceptibility testing for *Candida* for any positive culture requiring a change of antifungal therapy (i.e., identification and susceptibility testing not required for *Candida* isolates cultured from specimens obtained without a required change in antifungal therapy).

- All fungal isolates cultured from blood and normally sterile tissue/fluid must be sent to the Central Laboratory.
- Record the spp. for any new bacteria isolated from blood and the spp. and susceptibilities for any new bacteria isolated from any other normally sterile site.
- Record all concomitant medications.
- Record AEs.
- Presence of central line during Screening or placed during the study should be documented with dates and times of insertion and removal.
- Short-term central venous catheters (e.g., peripherally-inserted central catheters, internal jugular, or subclavian central venous catheters) and long-term central venous catheters (e.g., tunneled catheters) are recommended to be removed within 48 hours after diagnosis with candidemia, consistent with IDSA ([Pappas 2016](#)) and ESCMID ([Cornely 2012](#); [Ullmann 2012](#)) guidelines.
- If radiologic test is performed, record radiologic test type with Findings and Interpretation only if radiologic test provides evidence of invasive candidiasis or evidence of progression, stabilization, improvement, or resolution of invasive candidiasis from previous radiographs. Criteria for cure, indeterminate, and failure responses are found in [Table 10](#).

9.4.4 Days 23–28

- Administer study drug:
 - IV infusion of study drug over 60 (± 10) minutes (refer to [Section 8.0](#) and the Study Pharmacy Manual for additional infusion rate guidance). Administration should occur 24 (± 2) hours after study drug was administered on the previous day.

OR

- Oral step-down therapy.
- Clinical Assessments:
 - A focused physical exam (including a neurological exam) should be performed as clinically indicated by AE screening and course of the underlying disease.
 - Measure vital signs (temperature and the method used [oral, rectal, temporal, tympanic, or core], heart rate, blood pressure, and respiratory rate). Axillary temperatures are allowed, but not preferred.

- The retinal examination should be repeated in subjects who were negative at baseline if the subject develops visual signs or symptoms of a *Candida* eye infection during the study. Additionally, any neutropenic subjects who recover their neutrophil counts during the study should have an additional retinal examination. Subjects who were negative at baseline and are diagnosed with a *Candida* eye infection after initiating study drug must discontinue study drug (see [Section 7.4.2](#)) but may continue in the study at the Investigator's discretion; all subsequent antifungal drugs, interventions, and outcomes for endophthalmitis or chorioretinitis will be recorded.
- Laboratory Assessments:
 - Draw blood or normally sterile tissue/fluid (if possible) for culture if demonstrating mycological eradication (if not already done) or if clinically indicated.
 - Perform identification and susceptibility testing for *Candida* for any positive culture requiring a change of antifungal therapy (i.e., identification and susceptibility testing not required for *Candida* isolates cultured from specimens obtained without a required change in antifungal therapy).
 - All fungal isolates cultured from blood and normally sterile tissue/fluid must be sent to the Central Laboratory.
 - Record the spp. for any new bacteria isolated from blood and the spp. and susceptibilities for any new bacteria isolated from any other normally sterile site.
- Record all concomitant medications.
- Record AEs.
- Presence of central line during Screening or placed during the study should be documented with dates and times of insertion and removal.
- Short-term central venous catheters (e.g., peripherally-inserted central catheters, internal jugular, or subclavian central venous catheters) and long-term central venous catheters (e.g., tunneled catheters) are recommended to be removed within 48 hours after diagnosis with candidemia, consistent with IDSA ([Pappas 2016](#)) and ESCMID ([Cornely 2012](#); [Ullmann 2012](#)) guidelines.
- If radiologic test is performed, record radiologic test type with Findings and Interpretation only if radiologic test provides evidence of invasive candidiasis or evidence of progression, stabilization, improvement, or resolution of invasive candidiasis from previous radiographs. Criteria for cure, indeterminate, and failure responses are found in [Table 10](#).

10.0 ASSESSMENT OF EFFICACY

Efficacy assessments for all subjects occur on Day 5, Day 14 (± 1 day), Day 30 (-2 days), EOT (≤ 2 days of last dose), and the Follow-up visit (Days 52–59).

10.1 Primary Efficacy Outcome

The primary efficacy outcome for the FDA is ACM at Day 30 (-2 days). All attempts will be made to determine the survival status of all subjects at Day 30. However, if it is unknown whether a subject is alive or deceased, the subject will be considered deceased for the primary efficacy outcome.

The primary efficacy outcome for the EMA is global cure (based on clinical cure as assessed by the Investigator, radiological cure [for qualifying invasive candidiasis subjects], and mycological eradication) confirmed by an independent DRC at Day 14 (± 1 day). Global response is determined from the clinical response as assessed by the Investigator, radiologic response (for those subjects with invasive candidiasis documented by radiologic/imaging evidence at baseline), and mycological response at Day 5, Day 14 (± 1 day), Day 30 (-2 days), EOT (≤ 2 days of last dose) and Follow-up (Days 52–59) and confirmed by the DRC. The outcome of global response as determined by clinical response, radiological response, and mycological response is in Table 7. An independent blinded DRC will review subject data and confirm the determination of global response. The global response as determined by the DRC will be used for analysis. The role of the DRC and procedures for outcome determination are described in the DRC Charter.

Table 7: Global Response

Global Response	Definition		
	Mycological Response	Clinical Response as Assessed by the Investigator	Radiological Response**
Cure	Eradication/Presumed Eradication*	Cure	Cure
Failure	Eradication/Presumed Eradication *	Cure	Failure
	Eradication/Presumed Eradication *	Failure	Cure, Failure or Indeterminate
	Eradication/Presumed Eradication *	Indeterminate	Failure
	Failure	Cure, Failure or Indeterminate	Cure, Failure or Indeterminate
	Indeterminate	Failure	Cure, Failure or Indeterminate
	Indeterminate	Cure	Failure
	Indeterminate	Indeterminate	Failure
Indeterminate	Eradication/Presumed Eradication *	Cure	Indeterminate
	Eradication/Presumed Eradication *	Indeterminate	Cure or Indeterminate
	Indeterminate	Cure	Cure or Indeterminate
	Indeterminate	Indeterminate	Cure or Indeterminate

* Presumed eradication is defined only for a culture from a normally sterile site and is not defined for a blood culture.

** For those subjects with invasive candidiasis documented by radiologic/imaging evidence at baseline.

10.2 Secondary Efficacy Outcomes

All-cause mortality at Day 30 (-2 days) is a secondary outcome for the EMA, and global cure at Day 14 (± 1 day) is a secondary outcome for the FDA.

Additional secondary efficacy outcome measures are mycological eradication, clinical cure, and radiological cure (for those subjects with invasive candidiasis documented by radiologic/imaging evidence at baseline). Definitions for mycological eradication, clinical cure, and radiological cure are provided below in [Section 10.2.1](#), [Section 10.2.2](#), and [Section 10.2.3](#), respectively.

10.2.1 Mycological Response

Table 8: Mycological Response Definitions

Mycological Response	Definition
Eradication*	
 • If positive blood culture at baseline: 
 ○ The last blood culture drawn on or prior to the day of assessments is negative without a subsequent positive culture from a sample drawn following the first dose of study drug • If positive culture from a normally sterile site at baseline (other than blood): 
 ○ Documented mycological eradication: most recent culture on or prior to the day of assessment from all normally sterile sites of baseline Candida infection (if accessible) is negative and culture was obtained after the initiation of study drug, 
OR
 
 ○ Presumed mycological eradication: follow-up culture from all normally sterile sites of baseline Candida infection is not available (e.g., normally sterile baseline site of Candida infection not accessible) or the most recent culture from all normally sterile sites of baseline Candida infection obtained after the initiation of study drug is positive, in a subject with a successful clinical outcome as assessed by the Investigator (i.e., did not receive rescue antifungal treatment and has resolution of systemic signs and symptoms of invasive candidiasis that were present at baseline) and the subject has a successful radiological outcome (for those with documented evidence of disease from imaging at baseline), 
AND
 
 • There was no change of antifungal therapy for the treatment of candidemia and/or invasive candidiasis, 
AND
 
 • The subject is not lost to follow up on the day of assessment.

Mycological Response	Definition
Failure	
 • If positive blood culture at baseline: 
 ○ The last blood culture drawn on or prior to the day of assessment is positive for Candida spp. from a sample drawn following the first dose of study drug, OR • If positive culture from a normally sterile site at baseline: 
 ○ Documented mycological persistence: most recent culture on or prior to the day of assessment from all normally sterile sites of baseline Candida infection (if accessible) is positive and culture was obtained after the initiation of study drug, OR ○ Presumed mycological persistence: follow-up culture from all normally sterile sites of baseline Candida infection is not available (e.g., normally sterile baseline site of Candida infection not accessible) OR the most recent culture from all normally sterile sites of baseline Candida infection obtained after initiation of study drug is positive in a subject without a successful clinical outcome as assessed by the Investigator or without a successful radiological outcome for those with documented evidence of disease from imaging at baseline, OR • The subject requires a change of antifungal therapy to treat candidemia and/or invasive candidiasis, OR • The subject dies of any cause prior to or on the day of assessment.
Indeterminate	
Study data are not available for the evaluation of efficacy for any reason including:
 
 • If positive blood culture at baseline: A post-baseline blood specimen was not available to culture or the result was not available. • If positive culture from a normally sterile site at baseline: A sterile site/fluid post-baseline specimen was not available to culture or the result was not available AND an assessment clinical outcome by the Investigator was not available or radiographic assessments are not available. • Subject is lost to follow-up on the day of assessment.

* Presumed eradication is defined only for a culture from a normally sterile site and is not defined for a blood culture.

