Failure	
 • If positive blood culture at baseline: 
 ○ The last blood culture drawn on or prior to the day of assessment is positive for Candida spp from a sample drawn following the first dose of study drug, OR • If positive culture from a normally sterile site at baseline: 
 ○ Documented mycological persistence: culture on the day of assessment from all normally sterile sites of baseline Candida infection (if accessible) is positive, OR ○ Presumed mycological persistence: follow-up culture from all normally sterile sites of baseline Candida infection is not available (eg, normally sterile baseline site of Candida infection not accessible) OR the most recent culture from all normally sterile sites of baseline Candida infection obtained after initiation of study drug is positive, in a subject without a successful clinical outcome as assessed by the Investigator or without a successful radiological outcome for those with documented evidence of disease from imaging at baseline, OR • The subject requires a change of antifungal therapy to treat candidemia and/or invasive candidiasis***, OR • The subject dies of any cause prior to or on the day of assessment.
Indeterminate	
Study data are not available for the evaluation of efficacy for any reason including:
 
 • If positive blood culture at baseline: A post-baseline blood specimen was not available to culture or the result was not available. • If positive culture from a normally sterile site at baseline: A sterile site/fluid post-baseline specimen was not available to culture or the result was not available AND an assessment clinical response by the Investigator was not available or radiographic assessments are not available. • Subject is lost to follow-up on the day of assessment.

* Presumed eradication is defined only for a culture from a normally sterile site and is not defined for a blood culture.

**Table includes clarifications that are not in the protocol.

*** Defined as receipt of an antifungal with an indication of Candidemia/invasive candidiasis, *Candida* endophthalmitis/chorioretinitis or *Candida* endocarditis which started on or prior to the day of assessment or started on EOT (+ 1 day).

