3.2. General Methods

All tables, figures, and listings will be presented in landscape orientation in Courier New, 8-point font or higher, and will be incorporated into Microsoft Word, or Adobe Acrobat PDF files, sorted and labeled according to the International Conference on Harmonisation (ICH) recommendations, and formatted to the appropriate page size(s).

Categorical parameters will be summarized using frequencies and percentages, while mean, standard deviation, median, 25th and 75th percentiles, minimum, and maximum will be used for continuous parameters.

Decimal precision will be as follows:

- Mean will contain one more decimal place than actual values.
- Median will contain one more decimal place than actual values.
- Standard deviation will contain two more decimal places than the actual values.
- 25th and 75th percentiles, minimum, and maximum will have the same precision as the actual values.

All statistical testing will be 2-sided and performed at the 0.05 level unless otherwise noted. Since no inferential testing will be conducted for secondary efficacy outcome measures, no adjustment is needed for multiplicity.

The first day of study drug administration will be Study Day 1. Subsequent study days are counted as the number of consecutive calendar days thereafter.

Individual subject listings of all data represented on the eCRFs will be provided to facilitate the investigation of tabulated values and to allow for the clinical review of all efficacy and safety parameters. All data listings and tables displaying by-subject data that contain an evaluation date will display study day (Study Day).

If a safety laboratory result is reported relative to a lower/upper range of detection for an assay, for example “<10”, the numeric portion of the result (10) will be used for statistical analyses and the full result, including any symbols, will be provided in the subject listings.

Sample sizes shown with summary statistics are the number of subjects with non-missing values. Where individual data points are missing, categorical data will be summarized based on reduced denominators (ie, only subjects with available data will be included in the denominators), unless otherwise specified.

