4.3.2. Secondary Efficacy Outcomes

The secondary efficacy endpoints of clinical response as assessed by Investigator, mycological response (programmatically derived), radiological response (for subjects with invasive candidiasis documented by radiologic/imaging evidence at baseline) will be presented using the number and percentage of subjects with a response of cure (eradication for mycological response), failure, or indeterminate, displayed by treatment group in the mITT population at Day 5, Day 14 (± 1 day), Day 30 (-2 days), End of Treatment (≤ 2 days of last dose), and Follow-up (Days 52-59).

The number and percentage of subjects with a global response of cure, failure, or indeterminate (confirmed by the DRC) will be presented by treatment group in the mITT population at Day 5, Day 30 (-2 days), EOT (≤ 2 days of last dose) and Follow-up (Days 52-59). 95% CIs for the treatment differences in global cure will be determined.

Treatment differences in secondary efficacy endpoints will be assessed using 95% CIs calculated at Day 5, Day 14 (± 1 day), Day 30 (-2 days), End of Treatment (≤ 2 days of last dose), and Follow-up (Days 52-59). Two-sided 95% CIs will be constructed for the observed differences in the global cure, mycological eradication, radiologic cure and clinical cure rates using the method of Miettinen and Nurminen without stratification. The 95% CIs are for descriptive purposes only.

Analyses by diagnosis (candidemia only; invasive candidiasis) and APACHE II score/ ANC (APACHE II score ≥ 20 OR ANC < 500 cells/ μ L; APACHE II score < 20 AND ANC ≥ 500 cells/ μ L) at Screening will also be provided.

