6. CHANGES TO PLANNED ANALYSES

There are no changes between the protocol-defined statistical analyses and those presented in this SAP.

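### A positive sterile-site culture in a clinically successful subject is both Presumed Eradication and Documented Persistence; the SAP keeps the conflict for same-day cultures, and no precedence is stated

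*Protocol*

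**What the plan says.** **Protocol 10.2.1, Table 8.** In the Eradication row, Presumed Eradication has two limbs: no follow-up culture, or a most recent culture from the "infection obtained after the initiation of study drug is positive, in a subject with a successful clinical outcome as assessed by the Investigator". Both limbs also need radiological success where baseline imaging showed disease, no antifungal change, and a subject who is not lost to follow-up. In the Failure row, Documented Persistence takes the most recent culture on or before the assessment day from all baseline sterile sites and reads "if accessible) is positive and culture was obtained after the initiation of study drug". No clinical or radiological condition is attached.

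**SAP 2.2.2, Table 2-3.** The Presumed Eradication text is the same. The Failure row changes to "Documented mycological persistence: culture on the day of assessment from all normally sterile sites of baseline" infection being positive. A footnote says "Table includes clarifications that are not in the protocol". SAP Section 6 says "There are no changes between the protocol-defined statistical analyses and those presented in this SAP".

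**Use of the result.** SAP 4.3.2 lists "mycological response (programmatically derived") as a secondary endpoint and says of the secondary intervals: "The 95% CIs are for descriptive purposes only". SAP 3.2 adds: "Since no inferential testing will be conducted for secondary efficacy outcome measures, no adjustment is needed for multiplicity". Global response, the EMA primary endpoint, is determined by the DRC under its Charter (Protocol 10.1; SAP 2.2.1). The Charter is not among the documents.

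**The concern.** Two written rules give the same subject opposite classes. This is not a detail left open: each rule is complete, and they disagree. The secondary endpoint is derived by program, so the code must apply one row before the other, and neither document gives the order.

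The two documents also disagree with each other about a positive culture taken before the assessment day, although Section 6 of the SAP reports no changes.

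The row chosen could matter beyond the secondary endpoint. In protocol Table 7 and SAP Table 2-2, mycological Failure always gives global Failure, whereas Presumed Eradication with clinical cure and applicable radiological cure gives global Cure. None of the three EMA sensitivity analyses in SAP 4.3.1.1 (indeterminates as successes, unadjusted interval, CE population) varies this classification. An order settled after unblinding could be influenced by the results.

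**Working it through.** **Step 1. Apply both tables to one subject.** Take a subject with a single non-blood sterile site who is alive, not lost to follow-up, on unchanged antifungal therapy, and a clinical success. Radiology is successful or not applicable, and the most recent post-dose culture is positive.

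| Positive culture taken | Protocol Table 8 | SAP Table 2-3 |
|---|---|---|
| On the assessment day | Presumed Eradication and Documented Persistence | Presumed Eradication and Documented Persistence |
| Before the assessment day | Presumed Eradication and Documented Persistence | Presumed Eradication only |

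A full enumeration (culture negative, positive or unavailable; same-day or earlier; clinical success or not; radiology successful, unsuccessful or not applicable; therapy changed or not) finds no other double classification and no unclassified combination. Presumed Persistence does not overlap with Presumed Eradication, because it requires a clinical or radiological non-success.

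**Step 2. Can the order be read from the text?** In the protocol, if Eradication prevails, Documented Persistence adds nothing, because Presumed Persistence already covers positives without success. If Failure prevails, the positive-culture limb of Presumed Eradication is empty. Either order removes a written clause, so neither is implied. Under the SAP's same-day wording with Failure prevailing, both clauses keep some content: same-day positives fail, and earlier positives with success are eradicated.

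**Step 3. Scale (assumptions; the documents give no count).**
- Protocol 4.7.2 gives a Phase 2 invasive candidiasis share of 20.8%. Applied to the planned 184 mITT subjects: 0.208 × 184 = 38.3, about 19 per arm. An assumed 40% share gives 0.40 × 184 = 73.6, about 37 per arm. Affected subjects are a subset of these.
- One subject in an arm of 92 moves its rate by 1/92 = 1.09 points.

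**Step 4. If the DRC applied the tables literally.** Unadjusted Miettinen-Nurminen 95% lower bounds for the cure difference, 92 per arm, starting from 64 cures in each arm (64/92 = 69.6%, near the planned 70%):

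| Cures, rezafungin v caspofungin | Lower bound |
|---|---|
| 64 v 64 | -13.3% |
| 63 v 64 | -14.4% |
| 62 v 64 | -15.5% |
| 59 v 64 | -18.9% |
| 58 v 64 | -20.003% |
| 62 v 62 | -13.5% |
| 58 v 58 | -13.9% |

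Reaching the -20% margin from equal arms takes six net losses, all in the rezafungin arm. If the affected subjects fall to either arm with probability 0.5 and all become Failure, the chance that the bound reaches -20% is 0 for 4 subjects, 1.6% for 6 (0.5^6 = 0.0156) and 5.5% for 10. The planned EMA interval is stratified, so these figures are only illustrative.

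**The case against.** The best defence is that the labels imply an order. Documented rests on a result and Presumed on inference, both Documented clauses are qualified by site access, and Protocol 6.1.7 sends inaccessible sites to clinical outcome. On that reading, a positive result from an accessible site would be Failure. It does not hold as text, because the positive-culture limb of Presumed Eradication carries no access limit and a positive culture means that a specimen was obtained.

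Several other points do stand:
- The SAP removes the double classification for earlier positives.
- The secondary endpoint is descriptive and has no inferential testing.
- SAP 2.6 refers to mycological response as assessed by the DRC, so the committee makes its own assessment, separate from the program.
- The affected group is probably small. Under Protocol 6.1.7, sterile-site cultures continue only until the first negative, only from accessible sites, and drain fluid may be used for only 24 hours after tube placement.
- The Table 2-3 footnote does disclose clarifications, and whether a response definition belongs under a heading on statistical analyses can be argued. Even so, the timing change alters how a subject is classed, and a reader of Section 6 would not learn of it.

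A reader might infer that the EMA primary result is at risk. The documents do not support that: the DRC's determination is what is analysed, its Charter may contain a rule, and the six-subject case needs every affected subject in one blinded arm.

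**Conclusion.** The contradiction is real, and the plan is wrong as written. The protocol overlap covers any positive most recent post-dose sterile-site culture with clinical and applicable radiological success and unchanged therapy; the SAP overlap covers only same-day positives. The two documents class earlier positives differently, and no order is stated.

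The demonstrated consequence is limited to the programmed secondary mycological response. An effect on global cure would require the DRC to follow Table 7 or Table 2-2 with the conflict unresolved, which is possible but not shown. The non-inferiority conclusion is unlikely to turn on this alone. That judgement rests on few affected subjects, near-equal arms and a random split between blinded arms, none of which the documents can confirm. It should be fixed before unblinding, mainly so that the class is set by a written rule and not by programming order.

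**What to change.** Before unblinding:

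1. Keep the SAP's same-day wording for Documented Persistence. Add under Table 2-3 that a positive culture on the day of assessment is Failure even if Presumed Eradication is otherwise met. The positive-culture limb of Presumed Eradication then applies only to earlier positives. Do not pair a Failure-prevails rule with the protocol's most-recent-culture timing, which would leave that limb empty.
2. State that the SAP definition governs the analysis, list the difference from protocol Table 8 in SAP Section 6, and confirm that the DRC uses the same rule.
3. Add to SAP 4.3.1.1 a sensitivity analysis of mycological response, and of global cure as a programmed recoding of the DRC result. It covers all subjects with a positive most recent post-dose sterile-site culture, clinical and applicable radiological success, and no other Failure criterion. Count them once as Failure and once as Eradication, and report their number by arm and by same-day or earlier culture.

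**Cost.** One sentence under Table 2-3, a governing statement with its Section 6 entry, one check with the DRC, and two runs on existing data. A protocol amendment is needed only if the sponsor prefers to change Table 8.

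**Downsides.** Eradication and cure rates may be slightly lower. The class will depend on whether a culture happened to be drawn on the assessment day; the split by culture timing in item 3 shows how much that matters. Letting Failure prevail is a choice that the documents do not dictate, which is why the analysis is run both ways. The rule does not settle missing radiology or mixed results across several sites.
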